The intervention group for this study are those who will utilize the smartphone app to complete the home-based portion of physical therapy following TKA. The control group are those who have completed traditional home health physical therapy following TKA. Inclusion criteria for the study consists of participants aged 45 to 64, the participant will have undergone unilateral TKA, and the participant should be discharged directly to home from the hospital. Participant's data from the intervention group will be excluded from the study if they do not engage with the app within 24 hours of discharge from the hospital, if the participant neglects to engage with the app over any 24-hour period during the study, or if the participant is readmitted to the hospital at any point during the home bound portion of their recovery.

Subjective outcomes for the participants in the intervention group will be assessed by the Short MAC and objective outcomes will be assessed by measuring total knee ROM improvement. The intervention participants' self-reported frequency of app usage will be compared to the participants' outcomes to determine the dose-response of the app. The Short MAC has been previously shown to be a reliable, valid, and responsive indicator of qualitative improvement in a patient's functional status post-TKA and total hip arthroplasty (THA) by Whitehouse et al (1). Minimum important change for Short MAC has been found to be 7.9 points for small change, 8.4 points for medium change, and 12.1 points for large change (2). The total knee ROM

improvement in the treatment group will be compared against a control group of patients who have completed traditional home care from a variety of physical therapists following TKA.

The primary hypothesis is that the intervention group will show a statistically equal outcome to the control group, demonstrating the efficacy of a low-cost alternative to traditional home care. The null hypothesis is that the research group will not show a statistically equal outcome to the control group. The first alternative hypothesis is that the intervention group will show a statistically significant improvement over the control group. The second alternative hypothesis is that the control group will show a statistically significant improvement over the intervention group.

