Data for the control group will be taken from approximately 30 individuals aged 45 to 64 that have previously completed traditional home health physical therapy care from a variety of physical therapists following TKA. Data for the intervention group will be taken within 48 hours of being discharged from the hospital from approximately 30 participants who agree to use the smartphone app to complete the home-based physical therapy portion of their recovery from TKA. Intervention group participants will complete an introductory meeting with the physical therapist in-person to onboard the patient to the app and perform the initial data collection. Participants in the intervention group will be encouraged to engage with the app 3 to 5 times per day as able. The intervention participant will have the ability to communicate any questions or concerns to the Physical Therapist via e-mail or phone call throughout the homebound portion of their recovery. For safety monitoring, a physical therapist will contact the intervention group participant via phone or e-mail every 24 to 48 hours to ensure no adverse events have occurred. A final in-person meeting will occur between the Physical Therapist and the participant at the conclusion of the homebound portion of the participants' recovery for the purpose of final data collection. A two-tailed t-test for two independent groups will be used to compare the means for total ROM improvement between the intervention group and the control group. Data from the Short MAC will be used to describe the overall subjective effect of the intervention on the patient's functional abilities. The relationship between the Participants self-reported frequency of app usage and their combined subjective and objective outcomes will be used to understand the dose-response of the app. Information about dose-response will be integral in establishing guidelines regarding frequency of app usage for optimal results.

Conclusion

Traditional home health care for individuals recovering from unilateral TKA is expensive and provides a higher level of service than most individuals, aged 45 to 64, require. Use of smartphone technology has the potential to drive down costs while maintaining outcomes for this patient population. The proposed randomized controlled trial would determine the efficacy and proper dose-response of a smartphone app to reduce costs and maintain outcomes for the desired patient population compared to traditional home care.

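### Raters of knee ROM do not overlap between the arms, the app-arm final reading is not masked to baseline, and no common ROM method is required, so part of any ROM difference, or lack of one, could be a measurement effect.

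*Protocol*

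**What the plan says.** All of this is in the Methods section of the Protocol.

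- **App arm, first reading.** The participant has an "introductory meeting with the physical therapist in-person to onboard the patient to the app and perform the initial data collection".
- **App arm, last reading.** "A final in-person meeting will occur between the Physical Therapist and the participant at the conclusion of the homebound portion" of recovery, for final data collection.
- **App arm, in between.** For safety monitoring, "a physical therapist will contact the intervention group participant via phone or e-mail every 24 to 48 hours".
- **Control arm.** "Data for the control group will be taken from approximately 30 individuals aged 45 to 64" who "previously completed traditional home health physical therapy care from a variety of physical therapists following TKA".
- **Outcome and test.** In the app arm, "objective outcomes will be assessed by measuring total knee ROM improvement", and this improvement is compared with that of the controls. "A two-tailed t-test for two independent groups will be used to compare the means for total ROM improvement" between the two groups. The test has no rater term.

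The stated hope is that the app arm's outcome will be equal to that of the controls. No equivalence margin is given. The Protocol names no assessor independent of treatment, no rater common to both arms, and no single type of ROM or instrument.

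**The concern.** Knee ROM is read by hand and depends partly on the patient's effort and the examiner's encouragement. In the app arm the reader is a physical therapist involved in delivering the app, who knows the treatment. Nothing keeps the baseline value from that therapist at the final reading. In the control arm the readings were apparently made earlier, by other therapists. Whatever separates the two sets of readers then enters the comparison of arms, and recruiting more patients does not average it out.

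The stake is the trial's main conclusion, in either direction. A net shift in favour of the app could be reported as an app benefit. The same shift could cover a true app deficit and so support the finding of equality that the Protocol hopes for. A shift against the app could do the reverse. An analysis plan cannot repair this afterwards, because the control care is already finished. What can still be changed is how app-arm readings are taken and which control data are accepted.

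**Working it through.** The Protocol gives no SD, alpha, power or margin, so there is no stated figure to reproduce. From the Protocol: about 30 per arm (app arm: "approximately 30 participants who agree to use the smartphone app"), a change-score outcome and a two-sided t-test. Assumed here: alpha 0.05, ROM SD 15 degrees at each time, baseline-final correlation r from 0.3 to 0.7, no true app effect.

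**1. Can the analysis separate rater from arm?** Take one app-arm rater and ten control raters (assumed numbers), none serving both arms. The arm indicator plus 11 rater indicators make 12 columns, and the matrix has rank 11. The arm effect cannot be estimated apart from fixed rater effects. Several app-arm raters would not change this as long as none of them also measured controls.

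**2. What survives in a change score?** Let a rater read true ROM plus an offset. Measured improvement is (true final + offset at final) − (true baseline + offset at baseline).

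- Same rater, same method, stable habit: the two offsets are equal and cancel.
- Expectation at the final reading, or a change of rater, ROM type or instrument between readings: the offsets differ and the difference remains.
- A different ROM type in the two arms: the arms compare improvements in different quantities, so cancellation within a patient does not settle the matter.

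**3. What would a surviving net shift do?**

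SE of the difference in mean improvement = 15 × √(2(1 − r)) × √(2/30).

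False-positive rate = P(|Z + shift/SE| > 1.96).

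| r | SE (degrees) | net shift 3 degrees | net shift 5 degrees |
|---|---|---|---|
| 0.3 | 4.58 | 0.10 | 0.19 |
| 0.5 | 3.87 | 0.12 | 0.25 |
| 0.7 | 3.00 | 0.17 | 0.39 |

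For example, at r = 0.5 and a shift of 3, shift/SE = 3/3.87 = 0.77. The noncentral t with 58 degrees of freedom gives nearly the same ranges: 10 to 17% and 19 to 37%.

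Free of the assumed SD, with the shift expressed in SDs of the change score and the noncentral t: 0.1 SD gives 6.7%, 0.2 SD gives 11.9%, 0.3 SD gives 20.8% and 0.5 SD gives 47.8%.

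**4. Hidden deficit.** By symmetry, a true app deficit of 3 degrees measured without bias is declared significant about 10 to 17% of the time, and one of 5 degrees about 19 to 39%. A favourable net shift of the same size brings the expected difference to zero and the rejection rate down to 5%.

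**The case against.** The other side has a good deal of force.

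- **Constant habits cancel.** A reader might infer that any habit of the app therapist, such as always measuring passive ROM or always rounding up, moves the app-arm mean. It does not if the same therapist does it at both readings. This stands, and it narrows the point to what differs between readings or between arms.
- **Control therapists were probably not masked either.** Therapists measuring their own patients in routine care would usually know the treatment and the starting value. Only the net difference between arms matters, and the document shows neither its size nor its sign. This stands.
- **Some tempting readings go beyond the text.** A reader might infer that one therapist onboards, follows and re-measures every app patient. The safety contact is by an unspecified therapist and the number of app-arm therapists is not given. With several, personal habits partly average out and only a shared expectation moves the whole arm. A reader might also take it that controls come from charts, or that control patients each had two raters. The text says only that data are taken from people whose care is complete. A variety of therapists fits variation across patients at least as well as within them. Past measurement of the controls is a strong inference, since their baseline ROM must have been read before their care ended, but it remains an inference.
- **Low power alone would miss small deficits.** On the figures above most deficits of 3 to 5 degrees go undetected even without bias, so rater bias adds only part of that harm. This stands.
- **There is a larger problem.** The Study Design section calls the trial randomized, yet the controls have already completed care, which ties period and patient selection to arm as well. Resolving that would not by itself settle who reads ROM or by what method, so this point remains separate.
- **Silence on method is not an error in itself.** Agreed. The point rests on the described arrangement of readers, in which the lack of a common method matters.

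**Conclusion.** The point holds in a limited form. As described, raters do not overlap between arms, the app-arm reader is involved in delivering the treatment and is not masked to baseline, and no common ROM method is required. Shifts that arise between the two readings, and differences in method between arms, would be mixed with the app effect, and the planned t-test cannot separate them.

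The documents do not support saying that the bias favours the app, or that it has any particular size. The ranges of 10 to 17% (3 degrees) and 19 to 39% (5 degrees) show only what a net shift would do under an assumed SD of 15 degrees, r of 0.3 to 0.7, 30 per arm and alpha 0.05. The shifts themselves are also assumed. The arrangement is plain from the text and its effect is uncertain. This is an improvement that should be made because it is cheap, not a defect that alone invalidates the trial.

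**What to change.** Amend the Methods section as follows.

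1. In the app arm, the therapist takes and records the final ROM reading before seeing the baseline value.
2. Use one type of ROM (active or passive) and one instrument at both app-arm readings. Accept only control data that document the same type and instrument at both times.
3. Record a rater identifier for each reading where available, and repeat the comparison using only controls whose two readings share a rater.
4. State that these steps reduce the confounding of rater with arm but do not remove it, and limit the conclusion accordingly. App readings will still come from app-arm therapists and control readings from others, and withholding the baseline value does not mask treatment. A reader might take step 3 as separating rater from app effect; it cannot. Assessors blinded to arm and using one method in both arms would be stronger, but need concurrent controls.

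The cost is protocol wording and a filter on control data, with no extra visit or assessor. The downside is that some control data will not qualify, so more charts must be screened to reach about 30 controls. The filter also selects controls by quality of documentation. The numbers screened and excluded, with reasons, should be reported.

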
45 to 64. Over the past decade, the smartphone has become an integral part of most people's lives. The latest Pew Research Data from February 2018 shows that 73% of individuals aged 50 to 64 own a smartphone (8). Smartphones would allow the patient to have direct multimedia access to a prescriptive exercise program designed by a licensed Physical Therapist without an in-person home visit, as well as to have communication directly with their Physical Therapist through secure in-app messaging or e-mail. The patient would benefit by having reduced intrusion in their home environment, convenient access to their Physical Therapist and their Physical Therapist's plan of care, and financial savings due to the elimination of home health care services following TKA. The Physical Therapist would benefit from the ability to quickly interact with the patient to mitigate any adverse events and to efficiently assist a greater number of patients compared to traditional home-based physical therapy. Third-party payors would benefit from drastically reduced home care costs for those recovering from TKA.

Objectives

The primary objective will be to determine the efficacy of the app for those recovering from TKA compared to traditional home care during the home bound portion of the patient's recovery from TKA by comparing ROM improvement outcomes between the intervention group and the control, as well as measuring the subjective improvement in functional outcomes for the intervention group by using the Short MAC. A secondary objective of the study is to determine the relationship between the intervention participants' self-reported frequency of engagement with the app and their qualitative and quantitative outcomes, otherwise known as the dose-response.

Methods

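### Final ROM is taken at an undefined end of the homebound period and elapsed days are not counted, so slower recovery with the app may be partly or wholly hidden

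*Protocol*

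**What the plan says.** The timing rules are all in the Methods section of the protocol.

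- **App group, start:** "Data for the intervention group will be taken within 48 hours of being discharged from the hospital from approximately 30 participants". This is tied to the calendar.
- **App group, end:** "A final in-person meeting will occur between the Physical Therapist and the participant at the conclusion of the homebound portion of the participants' recovery". This is tied to an event. No day, window, maximum length or criterion is given, and nobody is named to decide when the event has happened.
- **Controls:** people "that have previously completed traditional home health physical therapy care from a variety of physical therapists following TKA". Neither a baseline day nor a final day is stated.
- **Outcome and analysis:** "objective outcomes will be assessed by measuring total knee ROM improvement", and "A two-tailed t-test for two independent groups will be used to compare the means for total ROM improvement". The outcome is a change score, not a rate, and the test has no term for days elapsed.
- **Aim:** "The primary hypothesis is that the intervention group will show a statistically equal outcome to the control group".

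The Objectives section sets the comparison "during the home bound portion of the patient's recovery from TKA by comparing ROM improvement outcomes between the intervention group and the control". The length of that period is not listed as an outcome anywhere.

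**The concern.** The protocol describes the homebound period as a portion of recovery. The natural reading is that a patient leaves it by getting better, though the protocol does not say so. If that reading is even partly right, the time of measurement depends on treatment and is correlated with the outcome: a patient who recovers slowly gets more days of exercise and healing before the final ROM is taken. Two groups recovering at different speeds could then be measured in much the same state, and the difference in speed would show only in the number of days taken, which the plan does not compare.

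This matters more than usual because the trial hopes to find no difference. A timing rule that absorbs a delay favours the desired conclusion, and delay is a plausible harm when in-person therapy visits are removed. It cannot be repaired at analysis from ROM alone, because this visit is the only follow-up ROM measurement stated for the app group.

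**Working it through.** The protocol gives no expected gain, SD, margin or homebound duration, so there is no figure of its own to reproduce. The calculations below use assumed inputs. They show mechanism and direction, not the size of any bias in this trial.

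**1. Mean difference as exit becomes more dependent on ROM.** Assumptions: home care gains 30 degrees in 14 days (30/14 = 2.14 degrees a day), the app is 25% slower (1.61 degrees a day), gain is linear, and the between-patient CV of the rate is 25%. Let w be the share of the exit time set by ROM reached:

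- exit day = w × (30 / rate) + (1 − w) × 14
- gain at exit = rate × exit day = 30w + (1 − w) × 14 × rate
- mean gain, home care = 30w + 30(1 − w) = 30
- mean gain, app = 30w + 22.5(1 − w)
- difference = −7.5 × (1 − w)

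| Exit set by ROM | Difference in mean gain | Mean days, home care v app | Extra days |
|---|---|---|---|
| not at all (w = 0) | −7.5 degrees | 14 v 14 | 0 |
| half (w = 0.5) | −3.75 degrees | 14.6 v 17.1 | 2.5 |
| wholly (w = 1) | 0 | 15.1 v 20.2 | 5.0 |

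The zero in the last row follows by construction, since exit is there defined as reaching 30 degrees.

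**2. What the t-test would see.** A second illustration uses different assumptions: 30 per group, two-sided alpha 0.05, home-care gain 2 degrees a day (SD 0.4), exit at a mean gain of 30 degrees (SD 8), measurement SD 5 degrees, fixed day 15, and 3,000 simulated trials per case. Each cell gives the mean difference and the share of trials with p < 0.05.

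| App slower by | Fixed day 15 | Exit half by ROM | Exit wholly by ROM |
|---|---|---|---|
| 20% | −6.0; 87% | −3.0; 39% | −0.1; 4% |
| 30% | −9.0; 99.8% | −4.5; 70% | 0.0; 5% |
| 40% | −12.0; 100% | −6.0; 91% | 0.0; 5% |

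In the last column detection is no better than the false-positive rate. Meanwhile mean time to assessment rises from 15.7 days to 19.6, 22.4 and 26.2.

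**3. Whether a fixed day alone solves it.** Return to the model of step 1 with a day-14 target, and suppose home-care records stop at exit. Controls with no entry near day 14 are then the fastest recoverers. Dropping and replacing them gives:

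- exit wholly by ROM, 1-day window: 62% of controls kept, visible difference −2.7 degrees
- exit half by ROM, 1-day window: 75% kept, visible difference −3.9 degrees, almost the same as the unfixed −3.75

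Keeping those controls with their last recorded ROM loses less. With exit wholly by ROM, a control's recorded gain is the smaller of 30 and the day-14 gain. The mean shortfall is 30 × 0.25 × 0.399 = 3.0 degrees (0.399 is the standard normal density at zero), so the control mean is 27.0 and the difference is 22.5 − 27.0 = −4.5. With exit half by ROM the shortfall is 15 × 0.25 × 0.399 = 1.5, the control mean is 28.5 and the difference is −6.0. Both still fall short of −7.5, so homebound duration has to be compared as well.

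**The case against.** The strongest objection is that the premise is an inference. The protocol never says what ends the homebound portion or that ROM plays any part. A visit allowance, a surgeon's follow-up date or simply being able to leave the house would each fit the wording. With a calendar or administrative end, the w = 0 row applies and this mechanism disappears. That stands, and it makes the bias conditional.

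A reader might go further and infer that the plan necessarily biases the comparison toward equality. The document does not support that. It would need both groups to be measured at the same recovery-related event, and no measurement time is given for the controls. The two groups' intervals may differ in either direction, making the app look better or worse as well as equal.

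It is also fair to say that measuring at the end of the phase matches the question in the Objectives, which is confined to the homebound period. That is a reason to keep the phase in view, but not a reason to leave its length uncounted. If the phase is the unit of comparison, how long it lasted is part of the result.

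Finally, a reader might infer that the dose-response analysis is distorted in the same way. That link is weaker, because the plan relates outcomes to self-reported frequency of use, not to total use over the period.

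**Conclusion.** The point holds in conditional form. The protocol fixes no time for the final ROM in either group, ignores elapsed days in the comparison and does not make homebound duration an outcome. Followed as written, the plan could report equal ROM improvement for an app that delays recovery, with nothing in the planned results to reveal it.

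The size is unknown. On the assumed inputs, a 7.5-degree deficit shrinks to between 3.75 and 0 degrees as the exit rule goes from half to wholly ROM-driven, and stays at 7.5 if exit does not depend on ROM at all. Even half dependence lowers detection of a 20% slower app from 87% to 39% with 30 per group. These results rest on linear gain and on the same exit rule in both groups, and the document confirms neither. The point should be settled before enrolment because the visit schedule cannot be changed afterwards.

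**What to change.** 1. Record the dates of surgery, of baseline ROM and of final ROM for every patient in both groups.
2. Make days to the end of the homebound portion a prespecified outcome, compared between groups alongside ROM improvement.
3. Hold the already planned final app-group visit on a prespecified day after surgery, with a window, and compare it with the control ROM entry nearest that day.
4. Do not replace controls whose records end earlier. Keep them with their last recorded ROM and its date, and state that this understates their gain by the fixed day.
5. Conclude equal outcome only if both ROM and duration are similar, with duration judged against a margin stated in advance, so that a trivial excess does not block the claim and a material one does.

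The cost is a change of protocol wording and a few dates per patient, with no extra visit. There are two downsides: some control records may have no ROM entry near the chosen day, and some app patients will be measured before or after their own homebound portion ends. The dates in step 1 make both visible.

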Traditional Home Health Physical Therapy Versus a Smartphone App for Patients Recovering from Total Knee Arthroplasty During the Home-bound Portion of Recovery: Study Protocol for a Randomized Controlled Trial

by [name] [name], PT, DPT

Study Design

Prospective randomized controlled trial comparing traditional home health care physical therapy to physical therapy provided via a smartphone app for patients recovering from total knee arthroplasty (TKA)

Background

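### The only between-group comparison is an unadjusted t-test of app volunteers against past home-care patients, so the estimated app effect may be confounded

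*Protocol*

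**What the plan says.** Under Methods, the comparison of the two groups is a single sentence: "A two-tailed t-test for two independent groups will be used to compare the means for total ROM improvement". The Short MAC and dose-response analyses use the app group only, so the t-test is the only between-group result.

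The groups are formed by different routes. For controls: "Data for the control group will be taken from approximately 30 individuals aged 45 to 64 that have previously completed traditional home health physical therapy". For the intervention: "approximately 30 participants who agree to use the smartphone app". The Study Design section calls the study a "Prospective randomized controlled trial comparing traditional home health care physical therapy to physical therapy provided via a smartphone app", and the Conclusion repeats the randomised label, but no allocation procedure is described.

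The stated eligibility criteria are age 45 to 64, unilateral TKA and discharge straight home. Sex, surgeon, hospital, calendar period and time since surgery are not restricted. The app group's first data are due within 48 hours of discharge; no window is given for the controls. Exclusions for non-engagement with the app apply to the intervention group, and the readmission exclusion is worded for that group only.

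**The concern.** A two-sample t-test credits the whole difference in means to the app. That is justified when the groups would have had the same average improvement under the same care. Randomisation would give this in expectation; choosing volunteers on one side and past patients on the other does not. A factor biases the comparison if it differs between the groups and is also related to ROM improvement. The test's p-value and confidence interval make no allowance for this.

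The primary hypothesis is that the app does as well as home care. Confounding could produce a false difference. It could also cancel a real app deficit, so that the groups look alike and home visits appear replaceable.

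This is not a detail left to a later analysis plan. The protocol names a method, and that method does not fit the comparison it describes.

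**Working it through.** **The plan's own figure.** The only design figure is about 30 per group. No significance level, SD, target difference or power is given, so it cannot be reproduced. For scale, assume a two-sided 5% level. The SE of the difference in SD units is sqrt(2/30) = 0.258, and 80% power needs a difference of about (1.960 + 0.842) × 0.258 = 0.72 SD.

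**Inputs.** From the protocol: about 30 per group and a two-tailed t-test (58 df). Assumed: a 5% level; independent patient factors, each with correlation r to ROM improvement and a between-group imbalance of D SD; an SD of ROM improvement of 12 to 20 degrees.

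**Bias and error rate with no true app effect.** Bias in SD units = r × D × number of factors, if all act in the same direction. Rejection rates come from the noncentral t with noncentrality bias/0.258.

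| r | D | Factors | Bias (SD) | Bias/SE | Rejection rate |
|---|---|---|---|---|---|
| – | – | none | 0 | 0 | 5.0% |
| 0.3 | 0.5 | 1 | 0.15 | 0.58 | 8.8% |
| 0.2 | 0.3 | 3 | 0.18 | 0.70 | 10.5% |
| 0.3 | 0.5 | 2 | 0.30 | 1.16 | 20.8% |

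In degrees, 0.30 SD is 0.30 × 12 = 3.6 to 0.30 × 20 = 6.

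**Sensitivity to direction.** If the signs are random, the two-factor case is half at 0.30 SD and half at zero: (20.8% + 5.0%)/2 = about 13%. The three-factor case falls to about 7%.

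**Masking.** Take a true app deficit of 0.5 SD and a bias of 0.30 SD in the app's favour. The expected difference is 0.5 − 0.3 = 0.2 SD. The chance of a significant result falls from 47.8% to 11.9%.

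**Does adjustment work for measured factors?** In simulation (30 against 30, no app effect, one covariate with D from 0.5 to 1.0 and r from 0.3 to 0.5, 4,000 runs per case), the t-test was biased by 0.15 to 0.50 SD and rejected in 9% to 47% of runs. The covariate-adjusted model had bias near zero and rejected in about 5%. With two factors at r = 0.3 and D = 0.5, the rates were 21% for the t-test and 4.7% with adjustment.

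**Price in precision.** For p uninformative covariates, the SE grows by about sqrt(57/(57 − p)): 1.027 for p = 3 and 1.037 for p = 4. If the covariates explain a share R² of group membership, multiply by 1/sqrt(1 − R²): 1.03 at 0.05, 1.12 at 0.20, 1.41 at 0.5 and 2.24 at 0.8.

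**The case against.** - **It follows from the design contradiction.** The study is labelled randomised, and under real randomisation the unadjusted test would not have this bias. That is correct. But correcting the label alone would leave the analysis sentence unchanged, so the sentence needs its own decision if past-patient controls stay.
- **Covariates belong in the SAP.** The choice of covariates often does, and the protocol does not forbid adjusted or sensitivity analyses. What stands against this is that the protocol already fixes an unadjusted test for a comparison whose described groups are not randomised.
- **No imbalance is shown.** A reader might infer that differences in age, sex, surgeon, hospital or timing definitely pass into the estimate. The documents do not support that. They report no imbalance on any of these, age is held to a 20-year band in both groups, and a factor matters only if it is also related to ROM improvement. This objection stands and limits the point to possible confounding.
- **The figures are assumptions.** This also stands. The larger ones need every factor to push the same way.
- **Adjustment has limits.** Surgeon, hospital or timing could nearly coincide with group, which would make the adjusted estimate very imprecise, or impossible to separate from the app effect if they coincide fully. This stands and shapes the remedy.

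**Conclusion.** The analysis should be changed if past-patient controls are kept. The protocol's sole between-group method leaves even measurable differences between volunteers and past patients in the estimate, so the app effect may be confounded, in unknown direction and by an unknown amount. The illustrative range of about 9% to 21% error rests wholly on the assumed correlations, imbalances and 5% level, and is not a prediction for this trial.

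Two stronger readings go too far. The documents do not establish that the result will be biased. Nor would covariate adjustment make the comparison equivalent to a randomised one: it addresses recorded factors, not willingness to use an app, unrecorded differences or the exclusions applied to app users only.

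**What to change.** If past-patient controls are kept, replace the t-test sentence in Methods along these lines:

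1. Primary analysis: a linear model of final ROM on group, baseline ROM and a short prespecified list of pre-treatment covariates recorded in both groups: age, sex, and days from surgery to first ROM reading. With baseline ROM in the model, the group coefficient is the same whether the outcome is final ROM or improvement, so the endpoint is not changed.
2. Use ordinary or small-sample (HC3) standard errors. The simplest robust version (HC0) rejected in about 6.6% to 7.3% of null simulations at this size.
3. Before fitting, tabulate the covariates by group and check overlap. Include surgeon or hospital only if both groups share them; otherwise report this as a limitation.
4. Report the adjusted difference with its confidence interval as the main result, and the t-test as an unadjusted secondary description.
5. State that self-selection, unmeasured confounding and the app-only exclusions are not removed.

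The cost is protocol wording and a few extra data fields. Age is already needed for eligibility, and an improvement score already requires a first ROM reading. The protocol does not say whether surgery dates are available for the controls, so this needs checking. The SE would be about 3% to 4% wider if the covariates prove uninformative, and wider still if they are strongly related to group.

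If the sponsor instead randomises, this change is not needed to remove the bias described here.
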